UAF will cede IRB approval to the UAMS IRB, though approved documents will be filed with the UAF IRB. Data gathered during the study will be kept on a password-protected device provided by UAF, which will be stored at the Engineering Research Center located at [name] and analyzed in the Biomedical Engineering department at UAF. The device will be stored in a secure location (Room #: 3407). A second copy of the data will be stored in a password-protected Box folder.

At the conclusion of the study, the data will be permanently de-identified. The data will be retained for a minimum of seven years after the study and final reporting are completed. It will thereafter be destroyed per all applicable UAMS institutional policies and federal regulations.

Title: Characterization of Preterm Neonatal Skin by Diffuse Reflectance Spectroscopy Pilot Study

Principal Investigator: [name], DNP, RNC-NIC

Sponsor: University of Arkansas for Medical Sciences (UAMS)

Data Analysis

Previous work has shown that the BiliChek results were very highly correlated to total serum bilirubin levels ($r = 0.88$) [9]. An *a priori* power analysis was conducted to determine the number of subjects needed to detect a similar strong correlation between the DRS and BiliChek data ($\alpha = 0.05$, power = 0.8, $r_0 = 0.7$, $r_1 = 0.85$; G*Power3.1). In this study, $n = 44$ completed subjects (≤ 37 weeks gestation at birth) will be recruited with the goal of maximizing biological variability (gestational age, sex, race/ethnicity) and validating our DRS system during the fewest visits possible. Subjects who have at least 1 measurement with both the BiliChek and DRS systems at a single anatomical location are considered completers of the study. Measured DRS spectra will be analyzed using a lookup table created from published absorbance spectra for each chromophore (e.g. hemoglobin, melanin, bilirubin) and the relative concentrations of the chromophores will be extracted [4]. The primary criteria for success will be a high, positive correlation ($r \geq 0.85$, Pearson's correlation coefficient) between the extracted DRS bilirubin concentration (dependent variable) and BiliChek-derived concentration (independent variable). The concentrations will be compared to blood oxygen saturation, weight, complete blood count, chemistry levels, lipids, liver profile, and blood gas, as available, by linear regression. In summary, the spectral and concentration data elements will be compared using linear regression and assessed using Pearson's correlation coefficient.

Ethical Considerations

This study will be conducted in accordance with all applicable government regulations and UAMS research policies and procedures. This protocol/ICF and any amendments will be submitted and approved by the UAMS IRB to conduct the study. All protocol and ICF amendments must be submitted to ORRA prior to IRB review.

The informed consent process will occur prior to any testing. The informed consent of each subject, using IRB-approved consent materials, will be obtained from the parent/LAR before the subject begins any study procedures. The parent/LAR of the subjects for this study will be provided the ICF on paper or electronically via email describing this study in language understandable to the study population. Consent materials will provide sufficient information for the parent/LAR to make an informed decision about their infant's participation in this study. The person obtaining consent will thoroughly explain to the parent/LAR important information about the study, including study requirements, study risks, and benefits. The consent process will take place on the maternity floor prior to the mother's discharge from the hospital or the patient's room in the NICU.

Privacy will be maintained throughout the consent process and questions regarding participation will be answered by the study doctor or staff. No coercion or undue influence will be used in the consent process. The ICF must be signed by the parent/LAR and the person obtaining the consent. The parent/LAR will receive a paper copy of the signed ICF and the informed consent process will be documented in the research record for each subject. A copy of the signed ICF will be placed in the subject's medical record.

The PI and study staff do not have or hold any financial conflict of interest or potential future financial interests in the investigational device involved in this study.

Dissemination of Data

Results of this study may be used for presentations, posters, or publications. The publications will not contain any identifiable information that could be linked to a subject. Furthermore, the study

Title: Characterization of Preterm Neonatal Skin by Diffuse Reflectance Spectroscopy Pilot Study

Principal Investigator: [name], DNP, RNC-NIC

Sponsor: University of Arkansas for Medical Sciences (UAMS)

will be registered and maintained in the ClinicalTrials.gov database, and results of this study will be submitted to ClinicalTrials.gov within one year of the study's completion date.

Title: Characterization of Preterm Neonatal Skin by Diffuse Reflectance Spectroscopy Pilot Study

Principal Investigator: [name], DNP, RNC-NIC

Sponsor: University of Arkansas for Medical Sciences (UAMS)

References

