Preterm neonates are plagued with an abundance of hardships, many of which are related to the incomplete development of their epidermis. The epidermal layer of the skin develops slowly and is still incomplete in the third trimester. For preterm neonates, this layer may not be fully developed at birth [1]. With an underdeveloped epidermis, the preterm infant can experience the following challenges: trans-epidermal water loss, trouble regulating temperature, and increased skin irritation or wounding from adhesives, prolonged contact with tubing, and frequent blood draws. Unfortunately, there are no quantitative methods of characterizing the development of the epidermis in preterm neonates. Furthermore, the means of assessing the development of a wound achieved by visual inspection can be highly subjective, depending on the provider performing the assessment. With the trend of a larger number of preterm infants surviving and at lower gestational ages, there is an urgent need for a quantitative method of characterizing the condition of preterm neonatal skin. This can increase the quality of care and decrease the risk of wound development. Previous work with optical spectroscopy has proven effective in the transdermal characterization of hemoglobin count, oxygen saturation levels, tissue scattering properties, and bilirubin levels [2,3]. However, no study or device has integrated this optical information to evaluate skin maturity and its susceptibility to injury in preterm neonates. Our long-term goal is to develop a non-invasive, quantitative means of characterizing the optical properties of neonatal skin that will be capable of evaluating skin status, guiding care and minimizing injury.

Objectives

The objective of this pilot study is to characterize the response of chromophores in preterm neonatal skin using diffuse reflectance spectroscopy (DRS) with the aim of understanding how the optical properties change with gestational age, race, ethnicity, and sex. This characterization will be used to develop novel methodologies to quantitatively analyze aspects of the stability of the infant.

Primary Objectives

1. Compare bilirubin concentrations derived from the DRS system with that collected from the Philip's BiliChek System using a linear regression and a Pearson's correlation coefficient assessment.

Secondary Objectives

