1. Compare bilirubin concentrations from the DRS to gestational age, race, ethnicity, and sex using a linear regression and a Pearson's correlation coefficient assessment.
2. Compare hemoglobin concentrations from the DRS to gestational age, race, ethnicity, and sex using a linear regression and a Pearson's correlation coefficient assessment.
3. Compare melanin concentrations from the DRS to gestational age, race, ethnicity, and sex using a linear regression and a Pearson's correlation coefficient assessment.

Study Population

Subject's gestational age, race, and ethnicity are expected to affect scattering properties and melanin absorption. Our analysis of DRS spectra will account for these parameters, which can be validated by extraction of bilirubin levels that match the BiliChek system measurements. Up to 80 subjects will be consented for a total of 44 completed subjects while inpatient in the University of Arkansas for Medical Sciences (UAMS) Neonatal Intensive Care Unit (NICU), noting current average daily census of 60 infants are cared for daily. A recruitment flyer will be posted at nurse's stations to advertise the study to families of potential subjects and provide information about how parents/legally authorized representative (LARs) can speak to a study team member about

Title: Characterization of Preterm Neonatal Skin by Diffuse Reflectance Spectroscopy Pilot Study

Principal Investigator: [name], DNP, RNC-NIC

Sponsor: University of Arkansas for Medical Sciences (UAMS)

enrolling their infants. Potential subjects will be identified in the UAMS NICU and maternal floor.

Recruitment of subjects will be performed by the Principal Investigator (PI) and delegated UAMS study staff who have routine access to patient schedules of NICU admissions by census review. Parents/LARs will be approached by or directed to the PI and/or delegated UAMS study staff for study details.

To the extent possible, the 44 completed subjects should be evenly distributed between males and females. Recruitment will pause for males or females when either begins to exceed 50% of the total population. Additionally, to the extent possible, the 44 completed subjects should be distributed across races and ethnicities so that no particular race or ethnicity is overrepresented. Recruitment will pause for a particular race or ethnicity if that race and/or ethnicity reaches 50% of the total intended completers (i.e., 22 of the planned 44 complete subjects).

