Eligibility Criteria

Inclusion Criteria

- Infants, \leq 37 weeks gestation at birth
- Current care provided by the UAMS NICU
- Parents/LARs must be able to provide written consent

Exclusion Criteria

- Entering palliative care
- Known diagnosis of liver disease
- On isolation precautions
- Approaching end-of-life
- On minimal stimulation protocol
- Any other condition, that in the opinion of the investigator, might interfere with the safe conduct of the study or place the subject at increased risk

Study Design and Procedures

This study is a cross-sectional pilot study to characterize the response of neonatal premature skin to DRS when excited with a white light source, and provide a baseline of how the collected spectra change with the maturation of the epidermal layer in the weeks to term gestation after birth by using a correlation analysis. It will be conducted in the UAMS NICU. A device employing related technology, the Philip's BiliChek System, is currently used to assess the level of bilirubin in infants with proven accuracy. As such, BiliChek readings will be taken as an evidenced-based practice reference along with DRS spectra. Accordingly, DRS spectra and BiliChek readings will be performed on consented study subjects admitted to the NICU. The pilot data will be used to evaluate whether DRS spectra can be used to extract optical information (scattering coefficient) related to skin maturity as well as hemoglobin, melanin, and bilirubin concentrations (mg/mL). DRS spectra will be compared to a lookup table created from published absorbance spectra (collected with a spectrophotometer) for bilirubin, hemoglobin, and melanin, and converted into relative concentrations for each chromophore [5,6,7]. The DRS-derived bilirubin concentrations and BiliChek-derived bilirubin measurements will be compared with the primary criteria for success being a high, positive correlation ($r \geq 0.85$, Pearson's correlation coefficient).

The following coded data will also be collected only once during a 24-hour window before and/or after DRS readings as routine standard of care to investigate correlations with the DRS spectra: blood oxygen saturation, weight, race, ethnicity, corrected age, gestational age, sex, most recent

Title: Characterization of Preterm Neonatal Skin by Diffuse Reflectance Spectroscopy Pilot Study

Principal Investigator: [name], DNP, RNC-NIC

Sponsor: University of Arkansas for Medical Sciences (UAMS)

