complete blood count (if available in the 24-hour window,), most recent chemistry levels , lipids, liver profile, and blood gas (all if available). No laboratory tests will be performed solely for study purposes. Data will only be collected if values are available as part of regular medical care.

Procedure

A prospective subject's parent or LAR will be provided with a copy of the informed consent form (ICF)/HIPAA Authorization, including details of the study in English. Non-English speaking parents/LARs will not be approached for the study. Study-specific questions will be directed to the PI.

The consent process will occur prior to any research procedures being carried out; although, medical records may be reviewed prior to consent solely to assess eligibility for the study. Eligibility confirmation and study procedures must be conducted within 7 days of obtaining consent. If study procedures are not completed in the 7-day timeframe, subjects must be re-consented and eligibility re-confirmed.

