The spectrometer is a portable device and will be placed in the NICU room with the subject. The entire procedure is not expected to take more than 15 minutes for both the BiliChek and DRS readings. Delivery of the excitation light to the subject is through a fiber-optic probe and only triggered once it is placed against the subject's skin. No adhesive or transmitting medium will be used. The light source and subsequent data collection are initiated by a foot pedal. As a precautionary measure, subjects will wear the same eye protection used in the NICU during blue light therapy. Since the light intensity of the DRS is low enough and does not pose any danger, the researchers and personnel in the room will not be required to wear eye protection. The expected total time exposed to the DRS light is less than 10 seconds.

Study staff will conduct a visual inspection of the subject's skin at each anatomical site every 2

Title: Characterization of Preterm Neonatal Skin by Diffuse Reflectance Spectroscopy Pilot Study

Principal Investigator: [name], DNP, RNC-NIC

Sponsor: University of Arkansas for Medical Sciences (UAMS)

hours (\pm 15 minutes) for 24 hours for possible adverse skin changes after the DRS readings. The visual inspection will be recorded using the Visual Inspection Tool, developed for this study to document any changes in skin. Qualified medical personnel will conduct the visual observation to assess intact skin per standard of care for any change using the unit-based Neonatal Skin Condition Score [8], to grade dryness, erythema, and breakdown. All skin observations or adverse events, regardless of relatedness to device, will be documented in the subject's electronic medical record, as well as on the study Adverse Event Log.

Investigational Device

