The PI will carefully monitor study procedures to protect the safety of research subjects, the quality of the data, and the integrity of the study. The engineers from University of Arkansas Fayetteville (UAF) will be responsible for data recording. Specifically, the optical instrument is connected to a password-protected laptop that controls the acquisition and storage of spectral data. All data files will be duplicated after the measurements are taken for each subject, and one copy will be zip archived. A CRC-32 checksum value will be generated for a subject's archived folder, and stored with the data in a password-protected, multi-factor-authenticated Box folder. The other copy of the data stored on the laptop will be electronically transferred to password-protected, multi-factor-authenticated UAF servers for processing and analysis using light-tissue interaction models with the program Matlab (version 2022b). The data analysis will be completed within 90 days from acquisition. All study subject materials will be coded by assigning a unique identifying number and will not include additional identifiers. The study demographics, bilirubin concentrations, and clinical lab results will be extracted from the subject's electronic medical record and/or the UAMS Power BI Reporting System NICU Reports. This information will be downloaded in an Excel spreadsheet for analysis on the password-protected device. All data gathered for the analysis and the results of the analysis will be kept in each subject's folder on the secure UAF servers. The key to the subject's coded file, as well as completed paper consent forms, will be kept in a locked file in the PI's office.

Readings for the study will be taken at the UAMS NICU; however, the device and a maintenance log will subsequently be taken to UAF for data transfer to UAF servers and device storage. The

Title: Characterization of Preterm Neonatal Skin by Diffuse Reflectance Spectroscopy Pilot Study

Principal Investigator: [name], DNP, RNC-NIC

Sponsor: University of Arkansas for Medical Sciences (UAMS)

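### The three secondary regressions have no term for age at reading, so the gestational-age slope mixes gestation at birth with the timing of a single reading

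*Combined protocol and SAP*

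**What the plan says.** All references are to the combined protocol and SAP.

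- **Objectives and Secondary Objectives.** The aim is "understanding how the optical properties change with gestational age, race, ethnicity, and sex". Objective 1 is to "Compare bilirubin concentrations from the DRS to gestational age, race, ethnicity, and sex using a linear regression" and a Pearson correlation. Objectives 2 and 3 repeat this for hemoglobin and melanin.
- **Study Design and Procedures.** The study is cross-sectional, but it is meant to give a baseline for how spectra change with "maturation of the epidermal layer in the weeks to term gestation after birth by using a correlation analysis".
- **Data collected (same section).** Items are taken once, within 24 hours of the DRS readings. The list runs "blood oxygen saturation, weight, race, ethnicity, corrected age, gestational age, sex, most recent" blood count and other laboratory results where available. Corrected age is there. Time since birth is not named, and phototherapy is not listed.
- **Eligibility Criteria and Procedure.** Entry depends on gestation at birth and "Current care provided by the UAMS NICU", with no limit on age at reading. There is one study episode per infant, within 7 days of consent. Under Ethical Considerations, consent may be taken on the maternity floor or in the NICU room.
- **Light therapy.** Procedure states that "subjects will wear the same eye protection used in the NICU during blue light therapy". This and a like sentence under Risks and Benefits are the only mentions. It is not an exclusion.
- **Data Handling and Recordkeeping.** "The study demographics, bilirubin concentrations, and clinical lab results will be extracted from the subject's electronic medical record" and/or a unit reporting system. No treatment item is named.
- **Data Analysis.** Further regressions use oxygen saturation, weight and available laboratory values. Corrected age is not among them.

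**The concern.** Two infants born at the same gestation but read weeks apart enter the secondary models with the same gestational-age value. The models therefore cannot separate what an infant was at birth from how far it has matured since. If infants of different gestation tend to be read at different postnatal ages, the slope absorbs part of the timing effect. This applies to all three chromophores.

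For bilirubin there is a second influence. Phototherapy is a treatment directed at the outcome of objective 1, it is evidently used on the unit, and the study dataset has no field for it.

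At stake is the reading of three descriptive secondary results. A slope reported as change with gestational age could be taken for a maturation effect when it partly reflects when the reading was made.

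**Working it through.** **1. The plan's own figure.** The sample size concerns the primary objective. Inputs from Data Analysis are alpha 0.05, power 0.8, null correlation 0.7 and alternative 0.85. The formula is

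n = ((z_alpha + z_power) / (atanh 0.85 − atanh 0.7))² + 3.

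The denominator is 1.2562 − 0.8673 = 0.3889. One-sided: (1.6449 + 0.8416)/0.3889 = 6.394, squared 40.89, plus 3 = 43.9, rounded up to 44. The plan's 44 is reproduced one-sided (two-sided gives 54.9, so 55). No gestational-age term enters, so the present point does not change it.

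**2. What the omitted term does.** Let G be gestation at birth, P postnatal age at the reading, and A = G + P the postmenstrual age at the reading. Suppose the outcome is a + bG + cP + error. With P left out, the fitted slope on G estimates

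b + c·δ, where δ = Cov(G, P)/Var(G).

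The slope equals b only if c = 0 or δ = 0. Nothing in the design makes δ zero, because the reading is tied to consent and not to birth. If the outcome follows maturity A alone with slope m, then b = c = m and the crude slope is m(1 + δ). It is too small if earlier-born infants tend to be read later (δ < 0) and too large in the opposite case. The documents give neither c nor δ.

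**3. Illustration under assumptions.** Take n = 44, normal variables and no true gestational-age effect. Assume the omitted variable (postnatal age or phototherapy) has correlation −0.3 to −0.7 with gestational age and −0.3 to −0.7 with the outcome. The crude correlation is the product of the two. Rejection rates are for a two-sided 5% test, from 20,000 simulated datasets per row. Race, ethnicity and sex are left out for simplicity.

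| With gestational age | With outcome | Crude correlation | Rejects, crude | Rejects, adjusted | Variance inflation |
|---|---|---|---|---|---|
| −0.3 | −0.3 | 0.09 | 8.8% | 5.0% | 1/(1 − 0.09) = 1.10 |
| −0.5 | −0.5 | 0.25 | 38.6% | 5.0% | 1/(1 − 0.25) = 1.33 |
| −0.7 | −0.7 | 0.49 | 93.4% | 5.1% | 1/(1 − 0.49) = 1.96 |

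The interval for the gestational-age coefficient widens by the square root of the inflation, 1.05 to 1.40 times, if the residual variance stays the same. It widens less if the added variable explains some of the outcome.

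**4. Whether the data exist.** If corrected age means postmenstrual age, P = corrected age − G. If it is counted from term, with term set at T weeks, P = corrected age + T − G. The protocol does not define corrected age, so the derivation is possible but not yet fixed. Phototherapy status cannot be derived from any listed item.

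**The case against.** The strongest reply is that the plan states no causal target. It is a cross-sectional pilot that compares quantities by regression and correlation, and a crude association in infants as found on the unit is a legitimate descriptive result. This stands, and it is why the slope should be labelled crude and not called wrong.

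Second, the maturation aim is worded for spectra, not for bilirubin concentration, and corrected age is collected so that correlations with the spectra can be examined. This is fair, but such a correlation does not adjust the gestational-age regressions, and no planned regression contains corrected age. If gestational age were meant as age at the reading, the maturation aim would be better served. However, it is listed beside corrected age, and eligibility uses gestation at birth, so that reading is unlikely.

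Third, phototherapy may lie on the path from gestational age to bilirubin. Slopes with and without it then answer different questions. This also stands: adjustment should be a sensitivity analysis, not the required main model.

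A reader might also infer four stronger things that the documents do not support:

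- **The slope is biased and may have the wrong sign.** No true slope, timing imbalance or treatment imbalance is given, so neither direction nor sign can be stated.
- **A distortion in bilirubin units can be quoted.** It would be the product of two assumed numbers, and the DRS output is described as relative concentrations.
- **Treatment can never be checked later.** Under Data Handling and Recordkeeping, a code key is kept and permanent de-identification comes only at the end of the study. The chart can be revisited until then.
- **The primary correlation is compromised.** It pairs two devices on the same infant in the same episode, and nothing in this point shows that it is affected.

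**Conclusion.** The point holds as a gap in the secondary models. Each infant is read once at an uncontrolled postnatal age, and the models for bilirubin, hemoglobin and melanin carry no term for it, although corrected age is already collected. The gestational-age slope then mixes gestation at birth with timing and cannot alone describe change in the weeks after birth. This conclusion assumes that gestational age means gestation at birth.

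The size is unknown. The range in the working, from a trivial to a large spurious correlation, depends wholly on the assumed correlations. The success criterion of r ≥ 0.85 and n = 44 are unaffected. The change is worth making because it is cheap and serves a stated aim. The phototherapy part is a lesser one: record it, and show what it does to the bilirubin slope.

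**What to change.** - **Data Analysis.** Add postnatal age at the reading as a covariate in the three secondary models, and report the gestational-age slope with and without it. If A = G + P, only two of gestational age, postnatal age and corrected age can enter together, so name the pair. With corrected age in place of postnatal age, the gestational-age coefficient becomes b − c and means something else.
- **Study Design and Procedures.** Define corrected age (postmenstrual, or counted from term with term stated) and gestational age, and give the formula for postnatal age.
- **Record extraction.** Add phototherapy status at the reading (on/off) to the listed data, collected before de-identification. This is a recording item only and changes no care.
- **Sensitivity analysis.** Report the bilirubin slope with and without phototherapy status. Label the unadjusted slope a crude association, and state that phototherapy may lie between gestational age and bilirubin.

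The cost is one extra record field, one degree of freedom for postnatal age and one more for phototherapy in the bilirubin sensitivity model, with somewhat wider intervals for the gestational-age coefficient at n = 44. Postnatal age needs no new data once corrected age is defined. No visit, procedure or sample-size change follows.

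### Secondary objectives 1 to 3 name Pearson's r against race and ethnicity; if either has three or more nominal categories, the size and sign of r depend on arbitrary numbering

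*Combined protocol and SAP*

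**What the plan says.** Under Secondary Objectives, the combined protocol and SAP lists three comparisons, one each for bilirubin, hemoglobin and melanin. The method wording is identical; the melanin objective reads "Compare melanin concentrations from the DRS to gestational age, race, ethnicity, and sex using a linear regression and a Pearson's correlation coefficient assessment". Race and ethnicity are thus named as variables to be assessed with Pearson's r, alongside linear regression.

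The Objectives section makes these relations part of the study's purpose, "with the aim of understanding how the optical properties change with gestational age, race, ethnicity, and sex". The Study Population section states an expectation that "gestational age, race, and ethnicity are expected to affect scattering properties and melanin absorption".

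On recruitment, Study Population asks that completers be "distributed across races and ethnicities so that no particular race or ethnicity is overrepresented", as far as this can be achieved. Recruitment pauses for a race or ethnicity once it makes up 22 of the planned 44 completers.

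The documents give no list or number of race or ethnicity categories, no reference group, no indicator coding and no ANOVA-type test. Study Design and Procedures does call the collected data coded. Data Handling and Recordkeeping shows that the word there means replacing identifiers with a subject number.

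**The concern.** Pearson's r measures a straight-line relation between two numeric variables. A nominal variable with three or more categories has no natural order or spacing, so someone must assign numbers before r can be calculated. Different assignments on the same data give different values of r. Entering race in the regression as a single numbered column would have the same fault.

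For a two-level variable any renumbering is a linear change of scale, so |r| is fixed and only the sign depends on which level has the higher number. Sex is therefore safe once its coding is stated, and so is race or ethnicity if recorded in two groups.

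At stake is the interpretability of one reported statistic for race and ethnicity in all three secondary objectives. Melanin is the plainest case, because the plan itself expects a relation there. A coefficient that can be reversed by relabelling cannot describe how an optical property differs between groups.

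**Working it through.** **The plan's own figure.** The documents compute no figure for the secondary objectives. The one sample-size figure, 44, belongs to the primary correlation (Data Analysis: alpha 0.05, power 0.8, r0 = 0.7, r1 = 0.85). It reproduces with the Fisher z formula and a one-sided alpha, although sidedness is not stated: (atanh 0.85 − atanh 0.7) × √(44 − 3) − 1.645 = 0.3889 × 6.403 − 1.645 = 0.845, a power of 0.80. It is used below only as the number of infants.

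**Inputs.** From the documents: n = 44 completers and a soft limit of 22 per group. Assumed: one averaged value per infant; three groups A, B and C of 22, 14 and 8; group means 0, 1.0 and 0.5 in within-group SD units; within-group sum of squares 44 × 1² = 44. The one-value assumption is needed because Procedure describes 20 to 40 DRS measurements per infant over four sites, and no section says how they are combined. Results are expected values, not simulated samples.

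**Indicator-coded model.**
- Grand mean = (22×0 + 14×1.0 + 8×0.5)/44 = 18/44 = 0.409.
- Between-group sum of squares = 14×1² + 8×0.5² − 18²/44 = 16 − 7.364 = 8.636.
- Total = 44 + 8.636 = 52.636.
- R-squared = 8.636/52.636 = 0.164, whatever labels the groups carry.

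**Pearson's r under each numbering.** With x the assigned number, r = Sxy/√(Sxx × 52.636).

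| Numbering | Sxx | Sxy | r |
|---|---|---|---|
| A=1, B=2, C=3 | 150 − 74²/44 = 25.545 | 40 − 74×18/44 = 9.727 | +0.265 |
| A=1, C=2, B=3 | 180 − 80²/44 = 34.545 | 50 − 80×18/44 = 17.273 | +0.405 |
| B=1, A=2, C=3 | 174 − 82²/44 = 21.182 | 26 − 82×18/44 = −7.545 | −0.226 |

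The other three numberings are these reversed, which flips each sign. The same 44 values therefore give six correlations: ±0.23, ±0.27 and ±0.41.

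**Range under other assumptions.**
- Groups 22/20/2, means 0/1.0/0.5: |r| from 0.37 to 0.44.
- Groups 22/11/11, means 0/1/2: |r| of 0.27, 0.41 or 0.64, against a single R-squared of 0.41.
- Four groups 22/12/6/4, means 0/1.5/0.7/0.3: |r| from 0.20 to 0.53.
- All 267 ways of assigning sizes of 2 to 22 (total 44) to three groups with means 0/1.0/0.5: the gap between largest and smallest |r| is 0.07 to 0.32, median 0.22. With means 0/0.5/0.25 it is 0.04 to 0.17, median 0.11. Both scans place the third mean midway between the other two.

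**Two-level check.** Groups 22/22, means 0 and 1: between-group sum of squares 11, total 55, r = ±√(11/55) = ±0.447. Only the sign depends on coding.

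**The case against.** The best defence is that each objective also names linear regression, which handles nominal variables correctly if they enter as indicators. The plan neither states nor excludes that, and nowhere says that categories will be numbered 1, 2, 3. Correlating each 0/1 indicator separately would also fit the wording. This stands as far as it goes: a careful analyst could carry out the plan soundly. But Pearson's r against race and ethnicity is a named method, and nothing steers the analyst away from numbering the categories.

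The second defence is that the trigger is unconfirmed. A reader might infer that the recruitment limit forces three or more categories, because two groups each held to 22 can make up 44 only at exactly 22/22. The documents do not support that as a proof. The spread is an aim to be met where feasible, and recruitment pauses rather than closes. The limit also counts completers, whereas Study Discontinuation and Withdrawal has data from incomplete subjects analysed too, with up to 80 consented. Three or more categories remain plausible, no more.

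A reader might also take the closing sentence of Data Analysis as a second instruction to correlate with nominal variables. It says "the spectral and concentration data elements will be compared using linear regression and assessed using Pearson's correlation coefficient". Its subject is spectral and concentration data, and the variables listed just before it are oxygen saturation, weight and laboratory results. It is weak support; the point rests on Secondary Objectives.

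**Conclusion.** The point holds in conditional form. If race or ethnicity is recorded in three or more nominal categories, the Pearson's r named in secondary objectives 1 to 3 has arbitrary size and sign. In the main illustration |r| runs from 0.23 to 0.41 with either sign, where indicator coding gives one R-squared of 0.16. Those values rest on the assumed group sizes and means and on one averaged value per infant. The dependence on numbering does not rest on them: it arises whenever three or more groups differ in mean, and its extent varies with the configuration.

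Two stronger readings should not be drawn. A reader might infer that findings of statistical significance will turn on the numbering. No test is set for these objectives, and any such effect depends heavily on the assumed means. A reader might also infer that the plan lacks an analysis of maturation, because the secondary objectives name neither corrected age nor the scattering coefficient. Study Design and Procedures already collects corrected age for correlation with the spectra and plans to "extract optical information (scattering coefficient) related to skin maturity as well as hemoglobin, melanin, and bilirubin concentrations", so no such analysis is missing.

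These are secondary analyses in a pilot, and the sample size was not set for them. The primary correlation and the figure of 44 are unaffected. The wording should still be corrected before analysis, because a named method would otherwise yield an uninterpretable number.

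**What to change.** In Secondary Objectives, and for consistency in Data Analysis:

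- Restrict Pearson's r to continuous variables, and to two-level variables with the coding stated so that the sign can be read.
- List the race and ethnicity categories. Where there are three or more, enter them as indicator variables with a named reference group in the linear regression already planned.
- Collapse sparse categories by a rule fixed before analysis.
- Report group differences with 95% confidence intervals, and an overall F test or partial R-squared.

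This changes wording only; the variables are already to be collected. The cost is a few degrees of freedom. With one value from each of 44 infants, a model with gestational age, sex, one ethnicity indicator and two race indicators leaves 44 − 1 − 5 = 38 residual degrees of freedom (37 with three race indicators). Race as a single numbered column would leave 39. Collapsing categories also loses detail on small groups.
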